8.2.2 Safety Endpoints

8.2.2.1 Primary Safety Endpoint

The primary endpoint is the rate of clinically relevant complications associated with CyPass Micro-Stent placement and stability as determined at 36 months. Specific device-related complications include:

- ≠ Failure to implant CyPass, defined as inability to successfully deploy or insert the CyPass.
- ≠ Clinically significant CyPass malposition, defined as CyPass positioning after deployment such that:
 - The device is not in the supraciliary space, or
 - There is a clinical sequela resulting from device position including, but not limited to:
 - ≠ Secondary surgical intervention to modify device position (eg, repositioning, proximal end trimming or explantation)
 - ≠ Corneal endothelial touch by device
 - ≠ Corneal edema leading to loss of BCDVA > 2 lines at the last postoperative visit, in comparison with preoperative BCDVA
 - ≠ Progressive ECL, defined as ongoing reduction in endothelial cell count of 30% or more relative to the screening ECD value, where 'ongoing reduction in endothelial cell count' is defined as losses continuing after Visit 5 (6 Month Follow-up)
 - ≠ Erosion of device through sclera
 - ≠ Device obstruction requiring secondary surgical intervention.

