Study investigators will be trained on CyPass Micro-Stent implantation prior to site activation. However, as a newly approved device, Alcon may have an expert observer present during implantation (Visit 00) to offer guidance to the Investigator on implantation of the device. The presence and activities of the Alcon observer will be described in the Informed Consent. The Alcon observer will be under the supervision of the Investigator and will not intervene with the standard of care provided to study subjects or make safety-related decisions or assessments.

Surgery will take place after the subject successfully completes all screening assessments and is confirmed eligible to participate in the study per inclusion / exclusion requirements, but not more than 42 days after the date of screening (Visit 0). Prior to surgery, the subject must be instructed to use the following topical medications perioperatively: a 4th generation fluoroquinolone, eg, moxifloxacin 0.5% QID; a steroid, eg, difluprednate 0.05% QID; and a non-steroidal anti-inflammatory, eg, nepafenac 0.1% TID.

All eligible subjects will undergo cataract surgery and receive implantation of the CyPass Micro-Stent. The following information will be captured at this visit:

- ≠ Type of anesthesia (for cataract surgery and CyPass implantation)
- ≠ Type, size, and location of incision
- ≠ Effective Phacoemulsification Time (EPT)
- ≠ Cumulative Dissipated Energy (CDE)
- ≠ Clock hour location of inserted CyPass Implant
- ≠ Duration of CyPass implantation portion of the surgery
- ≠ Viscoelastic used prior to CyPass implantation and/or during cataract surgery
- ≠ Type of IOL implanted (monofocal, multifocal, toric, etc.)
- ≠ Surgical complications, including any blockage of the lumen or malposition
- ≠ Number of CyPass implantation attempts, defined as penetration of the tissue plane between the ciliary body and the scleral spur
- ≠ Intraoperative AEs (for cataract surgery and CyPass implantation)
- ≠ Perioperative medications (topical hypotensive medications administered)

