13. Examine the assembly. Confirm the condition of the CyPass Micro-Stent and that the guidewire is fully exposed at the distal end (Figure 12-2). If either the CyPass Micro-Stent or the CyPass applier guidewire is damaged, do not use. Set aside for return to Alcon (refer to Section 13.1.2). Use a back-up CyPass System for implantation.

[figure not shown]
Figure 12-2 CyPass Micro-Stent Loaded onto CyPass Applier Guidewire

14. Examine the AC angle with the goniolens under the microscope. Take note of angle anatomy to identify the best implantation site. Avoiding the area of the anterior ciliary arteries at 3, 6, 9 and 12 o'clock may help reduce the possibility of significant bleeding.
15. Fill the AC with ophthalmic viscoelastic (OVD) and use additional OVD as necessary to maintain a deep, stable AC during the CyPass Micro-Stent implantation process.
16. Introduce the loaded CyPass applier guidewire tube through the cataract incision and advance towards the intended site of implantation until the guidewire tube and sleeve have cleared the incision. When crossing the AC, rotate the CyPass applier guidewire such that its curvature is parallel to the iris plane.
17. Position the CyPass applier guidewire radially toward the scleral spur/ciliary body interface. Care should be taken to align the curvature of the CyPass on the guidewire with the curvature of the sclera bordering the supraciliary space to reduce the possibility of encountering resistance during insertion. To gain access, place the distal end of the guidewire at the scleral spur/ciliary body interface and smoothly advance the guidewire through the tissue plane between the ciliary body and adjacent sclera to separate the ciliary body from the scleral spur at the point of implantation.
18. Continue to advance the guidewire until only the most proximal retention ring and the collar of the CyPass Micro-Stent are located in the AC (Figure 12-3). An additional confirmatory placement landmark is when the top of the CyPass Micro-Stent collar is even with Schwalbe's line. In this position, the distal tip of the CyPass Micro-Stent should be resting against the sclera in the supraciliary space anterior to both retinal and choroidal tissues.

Figure 12-3

CyPass Micro-Stent at Implant Site

19. Hold the CyPass applier stationary and carefully press the front button on the CyPass applier to retract the guidewire into the guidewire tube, leaving the Micro-Stent anchored between the sclera and ciliary body.

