20. Remove the CyPass applier from the eye.
21. If resistance is encountered or adequate implantation is not achieved at the initial implant site, implantation at a location at least 2 clock hours away from any area of ciliary body disinsertion can be considered if there is no significant iris trauma, the CyPass Micro-Stent remains properly positioned on the guidewire, and adequate hemostasis and visualization can be maintained. Make sure that the position of the patient's head and the tilt of the microscope allow adequate gonioscopic visualization of the angle structures. Increase magnification and fine focus the microscope as needed. Additional viscoelastic tamponade may be needed to assure hemostasis and maintain visibility during CyPass Micro-Stent implantation. Align the curvature of the CyPass on the guidewire with the curvature of the sclera bordering the supraciliary space to reduce the possibility of encountering resistance during insertion.
22. Termination of the procedure should be considered after 2 failed attempts at device placement or if adequate visibility cannot be maintained during implantation.
23. Use gonioscopy to confirm CyPass Micro-Stent position. Optimal position of the CyPass Micro-Stent is when only the collar and the first retention ring are visible in the AC. Anterior positioning with more than 2 retention rings visible in the AC can be associated with corneal endothelial cell loss. Posterior positioning such that the collar is not visible can be associated with reduced device effectiveness.
 - a. If the CyPass Micro-Stent appears to be too anterior, use the guidewire tube of the CyPass applier to gently push the device deeper into the supraciliary space until it is optimally positioned. If the proximal end of the CyPass Micro-Stent appears to be too posterior, use a micro-forceps to grasp the CyPass Micro-Stent collar and gently pull it into the AC until the implant is optimally positioned. Do not use the irrigation/aspiration (I/A) tip for CyPass Micro-Stent positioning.
 - b. If proper placement cannot be achieved, implant removal should be considered. Use direct gonioscopy visualization and supplementary viscoelastic for safe removal.

24. Since retained viscoelastic can lead to elevated IOP in the early postoperative period, irrigate and aspirate viscoelastic from the AC, taking care to avoid I/A tip proximity to the CyPass Micro-Stent.

NOTE: The flow of irrigation fluid near the Micro-Stent may cause implant movement.

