12.4 Discontinued Subjects

Subjects may be discontinued (exited) from the study early due to:

- ≠ Failure to meet protocol eligibility criteria prior to or during surgery
- ≠ Adverse event(s)
- ≠ Administrative reasons (eg, voluntary withdrawal, lost to follow-up)

Subjects who fail to meet protocol eligibility criteria prior to implantation will not be followed beyond the date of determination of ineligibility unless the reason for ineligibility is the occurrence of an adverse event. Subjects who are discontinued due to an adverse event occurring prior to implantation will be followed until resolution or stabilization of the event. Implanted subjects and subjects with failed implantation (inability to successfully deploy or insert the CyPass) will be followed until the planned end of study period.

Discontinued subjects who have been implanted or in whom implantation failed will not be replaced. Notification of a subject's early discontinuation should be made immediately to the sponsor and documented on the appropriate eCRF.

If a subject exits the study before completion of the final, planned study visit (Visit 8), the Investigator should make reasonable attempts to have the subject return to the site to perform early exit procedures. Early exit procedures are all study procedures to be conducted at Visit 8 (see Section 12.2.10).

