13 DEVICE DEFICIENCIES AND ADVERSE EVENTS

13.1 General Information

An AE is any untoward medical occurrence, unintended disease or injury, or untoward clinical signs (including abnormal laboratory findings) in subjects, users, or other persons, whether or not related to the investigational medical device (test article). Refer to the Glossary of Terms for categories of AEs, ADEs, and SAEs.

Figure 13-1 Categorization of All Adverse Events

[figure not shown]
[figure not shown]

Figure 13–2

Categorization of All Serious Adverse Events

13.1.1 **Intraoperative Adverse Events**

Anticipated intraoperative adverse events include, but are not limited to, the following cataract surgery and other intraoperative complications.

- a) Anterior capsule tear
- b) Choroidal detachment
- c) Posterior capsular rupture
- d) Vitreous in the anterior chamber
- e) Choroidal hemorrhage or effusion
- f) Cyclodialysis cleft – oversized
- g) CyPass non-implantation after penetration of the tissue plane between the ciliary body and the scleral spur
- h) Descemet's membrane break
- i) Hyphema obscuring the surgeon's view
- j) Inadvertent loss of vitreous not associated with the cataract procedure
- k) Inadvertent perforation of sclera
- l) Secondary ocular surgical intervention – AC lavage
- m) Significant corneal damage
- n) Significant iris injury or trauma
- o) Subconjunctival hemorrhage
- p) Zonular dialysis

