15.2.1 Intention to Treat

The intention to treat (ITT) analysis set will be defined as the set of study eyes for which a CyPass Micro-Stent implant is attempted; the ITT analysis set will be the primary analysis set for all study analyses.

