⁶ ECD may be requested in the fellow eye at follow-up on a case by case basis.

⁷ Visual field testing may be repeated between screening (Visit 0) and surgery (Visit 00), if needed.

⁸ UBM or OCT conducted if CyPass is not visible on Gonioscopy at two consecutive visits after Visit 3 (1 Month Follow-up). Images retained at site to demonstrate placement of CyPass.

11 Appendix B: Study Design

12 Appendix C: Data Sources

Endpoint	CRF	Comments
Primary Effectiveness Endpoint		
None		
Secondary Effectiveness Endpoints		
Mean change in IOP	Baseline: Intraocular Pressure_Glaucoma PostOp: Intraocular Pressure_Glaucoma_1	
Proportion of subjects with IOP reduction \geq 20% while using the same or fewer topical ocular hypotensive medications	Baseline: Intraocular Pressure_Glaucoma PostOp: Intraocular Pressure_Glaucoma_1 Ocular Hypotensive Medications	
Proportion of subjects who are not using ocular hypotensive medication with IOP \geq 6 mmHg and \leq 18 mmHg	Baseline: Intraocular Pressure_Glaucoma PostOp: Intraocular Pressure_Glaucoma_1 Ocular Hypotensive Medications	
Primary Safety Endpoint		
Failure to implant CyPass, defined as inability to successfully deploy or insert the CyPass.	Adverse Event(s) SX	Intraop - g) CyPass non-implantation (as defined in the protocol)

Endpoint	CRF	Comments
Clinically significant CyPass malposition, defined as CyPass positioning after deployment such that:		
The device is not in the supraciliary space, or	Adverse Event(s) SX	Postop - bb) CyPass device malposition - positioning after deployment such that the device is not in the supraciliary space (Specify)

Endpoint	CRF	Comments

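### SAP Appendix C takes failure to implant only from an adverse event code that requires tissue-plane penetration; the primary endpoint has no such condition, so an eye that fails earlier may go uncounted

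*SAP*

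**What the plan says.** **Endpoint.** Protocol 8.2.2.1 lists as the first primary complication "Failure to implant CyPass, defined as inability to successfully deploy or insert the CyPass". SAP 6.2 repeats this. Protocol 12.4 describes failed implantation in the same terms and says that "subjects with failed implantation (inability to successfully deploy or insert the CyPass) will be followed until the planned end of study period". None of the three requires penetration of tissue.

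**Data source.** SAP Appendix C gives one source for this component, the Adverse Event(s) SX form, with the comment "Intraop - g) CyPass non-implantation (as defined in the protocol"). In Protocol 13.1.1, intraoperative item g is "CyPass non-implantation after penetration of the tissue plane between the ciliary body and the scleral spur".

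**Analysis set.** Protocol 15.2.1 and SAP 2.1 define ITT as "the set of study eyes for which a CyPass Micro-Stent implant is attempted". Protocol 12.2.2 lists among the surgery data "Number of CyPass implantation attempts, defined as penetration of the tissue plane between the ciliary body and the scleral spur". Neither ITT definition refers to that item.

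**Other records.** SAP 4.5 sends surgical data to listings, and SAP 6.5.2 does the same for device deficiencies. Appendix C links neither to the primary endpoint.

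**The concern.** A programmer who follows Appendix C as written selects code g and nothing else for this component. Code g carries a condition that the endpoint does not. Eyes that fail before the tissue plane is entered therefore meet the endpoint but are not in the mapped source.

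The study has one hypothesis test, of this rate against 7%. Any loss from the numerator moves the result towards success. The target also rests on COMPASS counts, and Protocol 15.8 says that these, including the two failures to implant, correspond to the endpoint definitions. A code-g count could then set a narrower numerator against a benchmark built on the wider wording.

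**Working it through.** **1. Can such an eye arise?** In Protocol 12.2.2.1, step 16 is "Introduce the loaded CyPass applier guidewire tube through the cataract incision and advance towards the intended site of implantation". Penetration comes at step 17. Step 22 says "Termination of the procedure should be considered after 2 failed attempts at device placement or if adequate visibility cannot be maintained during implantation". The second ground in step 22 does not depend on an attempt having penetrated tissue. An eye can therefore be abandoned between steps 16 and 17.

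**2. Where does it go?**

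| Meaning of attempted in ITT | Denominator | Numerator through code g | Effect on observed rate |
|---|---|---|---|
| Penetration, as in Protocol 12.2.2 | Eye leaves | Eye leaves | x/n becomes (x−1)/(n−1) |
| Wider than penetration | Eye stays | Eye not counted | x/n becomes (x−1)/n |

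Both new rates are below x/n whenever x < n. On the first reading the eye is followed to study end under Protocol 12.4 but belongs to no analysis set, because ITT is the only set the SAP defines.

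**3. The plan's own figure.** Inputs from SAP 7: 360 eyes, target 7%, true rate 4%, one-sided exact test at 0.05. The success limit is the largest c with P(X ≤ c | n, 0.07) ≤ 0.05.
- n = 360: c = 17, P(X ≤ 17 | 0.07) = 0.0499, power P(X ≤ 17 | 0.04) = 0.802. The stated 80% is reproduced.

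**4. The test as it will be run.** SAP 6.2 divides by all ITT eyes, planned at 450.
- P(X ≤ 22 | 450, 0.07) = 0.0429: pass.
- P(X ≤ 23 | 450, 0.07) = 0.0649: fail.
- P(X ≤ 22 | 449, 0.07) = 0.0440: pass, when the 23rd event eye leaves both counts.

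**5. Effect of one uncounted event eye (an assumed number).** On either reading the limit on true events becomes 23 instead of 22.
- False success at a true 7%: P(X ≤ 22) = 4.3% becomes P(X ≤ 23) = 6.5%.
- A fail turns into a pass only at exactly 23 true events. P(X = 23 | 450, p) is 4.4% at p = 4%, 8.5% at 5%, 6.1% at 6% and 2.2% at 7%.

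**6. An assumed range.** Suppose the full endpoint rate is 7%, and a share q of eyes fails before penetration and is uncounted but stays in the denominator. False success is P(X ≤ 22 | 450, 0.07 − q): 6.5% for q = 0.25%, 9.5% for 0.5% and 18.7% for 1%. No value of q comes from the documents.

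**7. Scale.** Protocol 15.8 gives 14 events as 3.74%, so about 14/0.0374 = 374 eyes. Two failures to implant of any kind in 374 is 0.53%, or 2.4 per 450. The documents do not say whether those two came before or after penetration.

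**The case against.** The strongest reply has four parts.

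- **Attempt is defined.** A reader might infer that attempted has no meaning anywhere in the plan. That is not supported: Protocol 12.2.2 ties an attempt to penetration, in the same words as code g. If that definition governs ITT, code g covers every non-implanted ITT eye and the two counts agree. What stands is that the definition belongs to a surgery data item, that the ITT definitions do not cite it, and that eyes meeting the endpoint wording would then drop out of the analysis.
- **Appendix C is a data-source table.** SAP 6.2 and 6.2.2 carry the wide wording, the Appendix C row repeats it, and the code sits in a comments column without the word only. The form itself is not in the documents. This lowers confidence, but no other source is named.
- **The exposed group is narrow.** Eyes without a clear view of an open angle are exited before implantation starts, and a device found damaged at step 13 is replaced by a back-up system. A reader might also infer that inability to deploy, listed as a device deficiency in Protocol 13.1.5, is a large gap. It adds little, because deployment (step 19) normally follows penetration (steps 17 and 18).
- **The eye would be visible.** Attempts and surgical complications are recorded, the adverse event list is open-ended, surgery data and deficiencies are listed, and Protocol 15.1 has eyes assigned to analysis sets before lock. None of this puts the eye into the numerator under the mapping as written.

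A reader might further infer that the explantation and reintervention codes (ee and gg), mapped only to secondary endpoints, let other primary events escape. The documents do not support this: events of that kind that meet the endpoint are already reportable under code cc, which Appendix C does map.

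**Conclusion.** The mismatch between the endpoint wording and its only mapped source is in the text and should be fixed. Its direction is certain: following the mapping can only lower the observed rate. Its size is not known. The number of affected eyes may be zero, and one eye is an illustration, not an estimate. The COMPASS count cannot supply the figure, because the timing of those two failures is not given.

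On the assumptions of 450 ITT eyes and exactly one uncounted event eye, false success at a true 7% is 6.5% instead of 4.3%, which is above the stated 0.05. The documents do not support saying that the trial will miss failures, or that its type I error is in fact inflated. Confidence is moderate, because the case report form is not available and Appendix C could be read less strictly.

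**What to change.** Before database lock:

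1. In SAP 2.1, state that ITT includes every eye in which the loaded applier was introduced into the eye for implantation, whether or not the tissue plane was penetrated.
2. In Appendix C, derive failure to implant from the wording of Protocol 8.2.2.1 and SAP 6.2, using the surgery form and the Device Deficiency form as well as code g. Count each such eye that left surgery without a CyPass because it could not be deployed or inserted. State explicitly that abandonment for lost visibility after the applier was introduced counts. Do not count deficiencies resolved with a back-up system.

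This is a rule for classifying endpoint events; it changes no surgical instruction, endpoint or target. The cost is SAP wording, a little programming and review of a few surgery records, all from forms already in use. The downside for the sponsor is that the observed rate may be slightly higher.

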- v. Choroidal effusion requiring surgical drainage
- vi. Suprachoroidal hemorrhage
- vii. BCDVA loss of ≥ 2 lines from the best postoperative BCDVA

z) Elevated mean IOP ≥ 10 mmHg than the qualifying baseline mean IOP at or after 1 month postoperative

aa) CyPass device obstructed by iris, vitreous, lens, fibrous overgrowth, fibrin, or blood

bb) CyPass device malposition – positioning after deployment such that the device is not in the supraciliary space

cc) CyPass device malposition – positioning after deployment such that there is a clinical sequela resulting from device position including, but not limited to:

- i. Secondary surgical intervention to modify device position (eg, repositioning, proximal end trimming or explantation)
- ii. Corneal endothelial touch by device
- iii. Corneal edema leading to loss of BCDVA > 2 lines at the last postoperative visit, in comparison with preoperative BCDVA
- iv. Progressive ECL, defined as ongoing reduction in endothelial cell count of 30% or more relative to the screening ECD value, where ‘ongoing reduction in endothelial cell count’ is defined as losses continuing after Visit 5 (6 Month Follow-up)
- v. Erosion of device through sclera
- vi. Device obstruction requiring secondary surgical intervention

dd) CyPass device dislodgement or movement, without sequelae, where device movement is defined as a change by at least 1 in the number of CyPass rings visible that is not attributable to variations in gonioscopic viewing angle or illumination, changes in angle anatomy due to concomitant findings such as resolution of hyphema, change in anterior chamber depth, or development of focal peripheral anterior synechiae

ee) CyPass device explantation associated with CyPass placement and stability

ff) CyPass device explantation NOT associated with CyPass placement and stability

gg) Unplanned ocular surgical reintervention associated with CyPass placement and stability

hh) Unplanned ocular surgical reintervention NOT associated with CyPass placement and stability (other than paracentesis to relieve pressure prior to 1 week postoperative or Nd:YAG capsulotomy)

- ii) Significant ptosis
- jj) Atrophy/phthisis
- kk) Wound dehiscence/leak (persistent aqueous leak or fistula formation)
- ll) Subconjunctival hemorrhage
- mm) Chronic pain in the study eye present greater than 3 months postoperative
- nn) Significant foreign body sensation at or after 3 months postoperative
- oo) IOL subluxation

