 - ≠ Secondary surgical intervention to modify device position (eg, repositioning, proximal end trimming or explantation)
 - ≠ Corneal endothelial touch by device
 - ≠ Corneal edema leading to loss of BCDVA > 2 lines at the last postoperative visit, in comparison with preoperative BCDVA
 - ≠ Progressive ECL, defined as ongoing reduction in endothelial cell count of 30% or more relative to the screening ECD value, where 'ongoing reduction in endothelial cell count' is defined as losses continuing after Visit 5 (6 Month Follow-up)
 - ≠ Erosion of device through sclera
 - ≠ Device obstruction requiring secondary surgical intervention.

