6.2.2 Analysis Methods

The primary safety hypothesis will be tested with an exact one-sided binomial test with type I error 0.05. This endpoint will be summarized by numerator (number of eyes meeting the endpoint), denominator (number of eyes in the ITT set), and the rate of ITT eyes meeting the endpoint. In addition, a summary of each individual complication type included in the primary safety endpoint (and a listing of these complications) will be provided.

Otherwise, no formal statistical hypothesis testing is planned for this study.

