6.5.11 CyPass Explantation and/or Repositioning

A listing detailing subjects with CyPass explantation and/or repositioning will be provided. The listing will include the following variables: site-subject, age, sex, race, ethnicity, explantation or repositioning event, surgery date, study day, and reason. The data for this listing will be collected on the adverse events eCRF. Further details can be found in Appendix C: Data Sources.

7 Sample Size and Power Calculations

The performance target for the primary safety endpoint is 7.0%.

An evaluation of COMPASS (TMI-09-01) data showed that through 24 months of follow-up, there were two eyes with failures to implant and eight eyes with CyPass malposition events, respectively, corresponding to the above definitions. In addition, there were four eyes with documentation of three rings visible within the first postoperative week that likely would have undergone early secondary surgical intervention due to anterior CyPass positioning under the approach documented in the Instructions for Use (IFU). Inclusion of these cases would increase the number of observed events from 10 to 14 (3.74%, 95% confidence

interval: 2.1% – 6.2%). Of note, not all investigators documented the number of rings visible in the early postoperative period because this was not a study requirement (data regarding the number of rings is recorded for only 96 subjects at 1 Day and 139 subjects at 1 Week), so this number likely underestimates the number of subjects who would have been candidates for early surgical re-intervention under the new criteria described in the IFU.

Based on these considerations, the “true” event rate is assumed to be 4.0%, and the performance target is set to 7.0%. The following assumptions were used for the sample size calculation:

- ≠ Type I error = 0.05
- ≠ one-sided alternative

With a sample size of 360 subjects in the final analysis (unilateral implants only) and a performance target of 7.0%, assuming a true event rate of 4.0%, there is 80% power to reject the null hypothesis based on a one-sided alpha = 0.05-level exact test for a single proportion.

To allow for attrition over this 36-month study, a cumulative rate of up to 20% of subjects lost to follow-up is assumed, corresponding to a targeted implantation of 450 eyes in 450 subjects to achieve at least 360 eyes with 36 months of follow-up.

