
There is a clinical sequela resulting from device position including, but not limited to:
 
Secondary surgical intervention to modify device position (eg, repositioning, proximal end trimming or explantation)
 
Corneal endothelial touch by device
 
Corneal edema leading to loss of BCDVA > 2 lines at the last postoperative visit, in comparison with preoperative BCDVA
 
Progressive ECL, defined as ongoing reduction in endothelial cell count of 30% or more relative to the screening ECD value, where 'ongoing reduction in endothelial cell count' is defined as losses continuing after Visit 5 (6 Month Follow-up)
 
Erosion of device through sclera
 
Device obstruction requiring secondary surgical intervention.
		Postop - cc) CyPass device malposition - positioning after deployment such that there is a clinical sequela resulting from device position (as defined in the protocol) (Specify)
Secondary Safety Endpoints		
Rate of occurrence of sight-threatening adverse events including		

Endpoint	CRF	Comments
Persistent (at time of study exit) BCDVA loss of 3 or more lines compared to best BCDVA achieved during the course of study	Adverse Event(s) SX	Postop - b) Persistent BCDVA loss of 3 lines or more (as defined in the protocol)
Endophthalmitis	Adverse Event(s) SX	Postop - d) Endophthalmitis
Corneal decompensation	Adverse Event(s) SX	Postop - n) Corneal decompensation
Retinal detachment	Adverse Event(s) SX	Postop - p) Retinal detachment
Severe choroidal hemorrhage or detachment	Adverse Event(s) SX	Postop - t) Choroidal hemorrhage or choroidal effusion (as defined in the protocol) lasting longer than 1 month (Specify)
Aqueous misdirection	Adverse Event(s) SX	Postop - h) Aqueous misdirection
The rate of ocular secondary surgical interventions (SSI)	Adverse Event(s) SX	
Any one of these four:
 
Postop - ee) CyPass device explantation associated with CyPass placement and stability
 
Postop - ff) CyPass device explantation NOT associated with CyPass placement and stability
 
Postop - gg) Unplanned ocular surgical reintervention associated with CyPass placement and stability
 
Postop - hh) Unplanned ocular surgical reintervention NOT associated with CyPass placement and stability (as defined in the protocol)

Endpoint	CRF	Comments

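### SAP Appendix C builds the primary endpoint from AE codes g), bb) and cc) only, so positional surgery recorded solely under ee) or gg) would be missed

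*SAP*

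**What the plan says.** SAP 6.2 (and Protocol 8.2.2.1) defines the primary event by complication. One listed complication is "Secondary surgical intervention to modify device position (eg, repositioning, proximal end trimming or explantation").

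SAP Section 12, Appendix C, then names the data source for each endpoint. The primary rows point to one adverse event code each:

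- failure to implant: "Intraop - g) CyPass non-implantation (as defined in the protocol");
- device not in the supraciliary space: code bb);
- clinical sequela of device position: "Postop - cc) CyPass device malposition - positioning after deployment such that there is a clinical sequela resulting from device position".

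The AE list in Protocol 13.1.2 has two further codes tied to the same concept: "ee) CyPass device explantation associated with CyPass placement and stability" and "gg) Unplanned ocular surgical reintervention associated with CyPass placement and stability". In Appendix C these appear only under the two secondary endpoints on ocular secondary surgical interventions (SSIs).

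SAP 6.2.2 fixes the test: "The primary safety hypothesis will be tested with an exact one-sided binomial test with type I error 0.05". The performance target is 7%, and no other hypothesis test is planned.

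**The concern.** Stent removal or repositioning because of its position is a central event for this study. A site that explants a malpositioned stent finds at least two codes that describe what it did: cc), which feeds the primary endpoint, and ee), which does not. For a repositioning or trimming the choice is between cc) and gg). The wording of ee) and gg) echoes the title of the primary endpoint, so choosing them would be an understandable decision rather than a careless one.

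If only ee) or gg) is recorded, the eye appears in the secondary rate of placement-and-stability SSIs and, for an explantation or repositioning, in the listing of SAP 6.5.11. In the primary test it counts as event-free. The secondary rate could then include eyes that meet the primary definition but are absent from the primary numerator. Any such loss lowers the observed complication rate and makes it easier to meet the target.

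**Working it through.** **Step 1. Compare the definition with the derivation.**

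| Event | Meets SAP 6.2? | Codes that fit (Protocol 13.1.2) | Feeds the primary endpoint in Appendix C? |
|---|---|---|---|
| Explantation because of position | Yes | cc) item i; ee) | cc) yes; ee) no |
| Repositioning or trimming | Yes | cc) item i; gg) | cc) yes; gg) no |

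Appendix C lists alternative codes where it intends them: four for the overall SSI rate (ee, ff, gg, hh) and two for the placement-and-stability SSI rate (ee, gg). The primary rows offer none. A programmer following the table would not pick up ee) or gg).

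**Step 2. Look for a rule that closes the gap.** SAP 6.5.1 says that the investigator selects an event category. Protocol 13.3.1 lets the sponsor upgrade seriousness or causality, but does not mention changing the category. SAP 6.5.11 produces a listing without linking it to the primary numerator. No section gives precedence between cc) and ee)/gg), requires both, or reconciles them.

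**Step 3. Reproduce the plan's own figure.** Inputs from SAP Section 7: target 7%, assumed true rate 4%, one-sided 0.05, n = 360, stated power 80%. The critical value c is the largest integer with P(X ≤ c | n, 0.07) ≤ 0.05, and power is P(X ≤ c | n, 0.04). The SAP 6.2 denominator is the ITT set, planned at about 450 eyes, so both sizes are shown.

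| n | c | c/n | Exact alpha | Power at 4% | p-value at c + 1 |
|---|---|---|---|---|---|
| 360 | 17 | 4.72% | 0.0499 | 0.802 | 0.078 (18 events) |
| 450 | 22 | 4.89% | 0.0429 | 0.860 | 0.065 (23 events) |

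The stated 80% is reproduced. If 18 of 360 eyes (or 23 of 450) truly had an event and one was filed only under ee) or gg), the test would pass when it should fail.

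**Step 4. Illustrate the size.** Let m be the share of true primary events recorded only under ee) or gg). The documents give no value, so m is an assumption. If each event is missed independently with probability m, the chance of passing at a true 7% rate is P(X ≤ c | n, 0.07 × (1 − m)). Expected true events are 0.07 × 360 = 25.2 and 0.07 × 450 = 31.5.

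| m | Eyes missed on average (n = 360; 450) | Chance of passing, n = 360 | Chance of passing, n = 450 |
|---|---|---|---|
| 0 | 0; 0 | 5.0% | 4.3% |
| 5% | 1.3; 1.6 | 8.2% | 7.5% |
| 10% | 2.5; 3.2 | 12.8% | 12.6% |
| 20% | 5.0; 6.3 | 27.8% | 29.7% |

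**The case against.** The best answer is that Appendix C already has a primary code for these operations. Item i of cc) in Protocol 13.1.2 names repositioning, trimming and explantation, and Appendix C prints the same wording next to cc). The two codes are not declared mutually exclusive, and Protocol 13.3 requires all ocular adverse events to be reported. A malposition and the surgery that treats it can thus be read as two entries. SAP 6.2 defines the numerator by complication, whereas Appendix C is a data-source table with the codes in a comments column. The Manual of Procedures or the data validation plan, neither of which is available here, may hold a coding rule. The component summary, the secondary SSI rate and the explantation listing would make a mismatch visible.

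Much of this stands. A reader might infer that a removed or repositioned stent never counts as a primary event. The documents do not support that, because an eye filed under cc), alone or with another code, counts. Nor do they support the idea that repositioning has a code of its own: it is named in cc) item i and otherwise falls in the general code gg). That sites would prefer ee) or gg) is plausible but not shown.

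What the objection does not supply is a rule. Dual entry is permitted, but it is not required in either document. Visibility in a listing does not move an eye into the numerator.

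**Conclusion.** The point holds as an unreconciled overlap between cc) and ee)/gg) that creates a risk of undercounting, not as a certain exclusion. The risk runs in one direction, towards passing, and it affects the only hypothesis test in the study. One missed eye is enough to reverse a result at the boundary.

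The 7.5% to 30% range rests entirely on an assumed 5% to 20% of events being recorded only under ee) or gg). It should not be read as the actual type I error of the plan: with consistent cc) coding the test keeps its 4.3% to 5.0%. The stated sample size and power are not in question.

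Positional surgery does matter to the benchmark. Of the 14 COMPASS eyes cited in SAP Section 7, 4 were included because they would probably have had early secondary surgery. That says nothing about the misfiled share, but it is a reason for the numerator here to capture such surgery fully.

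**What to change.** In SAP Appendix C, derive the primary endpoint from g), bb) and cc), plus every ee) or gg) record that meets the SAP 6.2 definition, counted once per eye. Before database lock, reconcile all ee), ff), gg) and hh) records against that definition; ff) and hh) are included because a positional surgery could have been filed there by mistake. Show the component table by code, so that readers can see which events entered by which route.

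Adding every gg) record automatically would be simpler but could over-count, since not every reintervention linked to placement and stability need meet the primary definition. Hence the check of each record.

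The cost is a few lines of SAP text, minor programming and a short record review. Sample size, alpha and planned power do not change. The observed rate can only stay the same or rise.
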